13.2.3 Statistical Analysis of Pharmacokinetics

Plasma drug concentrations and pharmacokinetic parameters will be presented in tabular and graphical form. Pharmacokinetic parameters of interest, such as apparent volume of the central compartment (Vc/F), elimination rate constant (Ke), half-life (t1/2), apparent oral clearance (CL/F), and area under the plasma concentration time curve (AUC) will be estimated using compartmental methods. Dose proportionality in pharmacokinetic parameters will be investigated by performing one-way analysis of variance (ANOVA) on dose-normalized parameters.

In addition to estimating individual pharmacokinetic parameters, we will also estimate the population parameters using nonlinear mixed effects modeling methods (NONMEM). This method estimates the population parameters and both the inter- and intra-subject variability. Once the population parameters and corresponding covariance matrix are estimated, individual estimates can be obtained using post hoc analysis.

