2.2.3.2 Pharmacology/Pharmacokinetics/Correlative Biological Studies

Pharmacokinetic data from children enrolled onto PBTC-027 (Table 2) showed that, based on $AUC_{0->12hr}$ and steady state C_{max} , pediatric ABT-888 drug exposure at 15 mg/m² is similar to adult dosing at 20 mg bid, and pediatric ABT-888 drug exposure at 20 mg/m² bid is slightly lower than adult dosing at 40 mg bid (AUC_{0->12hr} 1.55 µg•hr/mL in 1 child vs 1.87 +/- 0.49 µg•hr/mL in 3 adults). Based on maximally effective AUC_{0->24hr} of 3 µg•hr/mL predicted from animal models and observed AUC_{0->24hr} of 3.74 µg•hr/mL in adults receiving ABT-888 at 40 mg bid, it appears that pediatric dosing of 20 mg/m² bid or higher would be required to match the drug exposure seen in adults receiving 40 mg bid. Furthermore, PARP inhibition in PBMCs from children on PBTC-027 was highly variable, averaging only 31.5 +/- 33.6% inhibition in seven patients.

Table 2								
Pharm	Pharmacokinetic Data, PBTC-027 versus Adult Mean ± Standard Deviation							
	PBTC-027 PBTC-027 Adult Adult 20 mg/m ² 15 mg/m ² 40 mg bid 20 mg bid (22 mg/m ²) (11 mg/m ²)							
Number of patients	Number of patients1633							
AUC _{0->12hr} (μ g•hr/mL) 1.55 1.05 ± 0.42 1.87 ± 0.49 0.99 ± 0.37								
Steady State C _{max} (ng/ml)	379	222 ± 64	348 ± 55	171 ± 39				

Т	a	bl	ما	2
	а	U.	IV.	4

Based on the preliminary PK and pharmacodynamic data from PBTC-027, the trial was amended in an effort to optimize ABT-888 drug exposure and PARP inhibition. The revised treatment schema is as follows:

Revised Treatment Schema								
Dose Level	ABT-888 Dose, mg/m ² /dose BID	TMZ Dose, mg/m ² /dose daily x 5						
Dose Level	x 5 days	days						
0	15 mg/m ² /dose BID	135 mg/m ² /day						
1 (starting dose level)	20 mg/m ² /dose BID	135 mg/m ² /day						
2	25 mg/m ² /dose BID	135 mg/m ² /day						

Table 3

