5.1.1.2 Dose Escalations during ABT-888 and Irradiation

Dose Level 1 of ABT-888 during radiation treatment will be approximately 80% of the adult dose of 100 mg bid, which has been well tolerated. It is also expected that the 150 mg bid dose level in adults will be declared tolerable shortly. Dose escalation/de-escalation will be done using a standard phase I, 3 + 3 design in increments of approximately 30% (see Table 10 below). If the adult dose of 150 mg bid with radiation has been declared tolerable by the time this trial begins patient accrual, and the starting dose level of 50 mg/m² bid is also tolerated in children, we propose to proceed from dose level 1 directly to dose level 3 (85 mg/m² bid, equivalent to the adult dose of 150 mg bid). If dose level 3 is not tolerated, then we will de-escalate to dose level 2. If dose level 3 is tolerated, we will study dose level 4 only if supported by adult clinical data and PBMC PARP inhibition data from our ongoing trial.*

Table 10 ABT-888 Dose Levels During Radiation, Phase I of the Study					
Dose Level ABT-888 dose (mg/m ² /dose BID), M-F					
0	35 mg/m ² /dose BID				
1 (starting dose level)	50 mg/m ² /dose BID				
2	65 mg/m ² /dose BID				
3	85 mg/m ² /dose BID				
4 (pending supporting data)*	110 mg/m ² /dose BID				

There will be no intra-patient dose escalation during the irradiation phase of the study (ABT-888 and radiation treatment). Phase I of the study will be completed when MTD/recommended phase II dose of ABT-888 that can be safely administered with radiation has been determined.

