13.3 Projected Accrual Rate and Study Duration

Phase I

The projected accrual rate is 1.5-2.5 patients per month, based on knowledge of the member institutions and their commitment to the Consortium. With 2-3 likely dose levels, the total sample size and the study duration are expected to be 12-18 and about 1.5-2.0 years, respectively. The estimated duration incorporates the planned accrual suspensions for routine toxicity monitoring.

Phase II

The projected accrual rate is 1.5-2.5 patients per month, based on knowledge of the member institutions and their commitment to the Consortium. The total sample size and the study duration are expected to be approximately 60 patients and about 2-3.5 years. The table below is for both phases (Phase I and II combined)

I ab						
Expected: Nun	iber of Subjects					
Ethnic Category		Sex/Gender	•			
Ethnic Category	Females	Males	Total			
Hispanic or Latino	5	5	10			
Not Hispanic or Latino	33	23	56			
Ethnic Category: Total of All Subjects *	38	28	66			
Racial Categories						
American Indian / Alaska Native	1	0	1			

Table 21	
----------	--

Asian	2	2	4
Native Hawaiian or Other Pacific Islander	0	0	0
Black or African American	5	3	8
White	30	23	53
Racial Categories: Total of All Subjects*	38	28	66

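### The dose-proportionality test in section 13.2.3 does not say which parameters are dose-normalised and yields no estimate, so with 12-18 Phase I patients a non-significant ANOVA would not be evidence of proportionality

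*Combined protocol and SAP*

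**What the plan says.** Section 13.2.3 first names what will be estimated: "Pharmacokinetic parameters of interest, such as apparent volume of the central compartment (Vc/F), elimination rate constant (Ke), half-life (t1/2), apparent oral clearance" and AUC, by compartmental methods. It then says: "Dose proportionality in pharmacokinetic parameters will be investigated by performing one-way analysis of variance (ANOVA) on dose-normalized parameters". It gives no list of the parameters to be normalised, no scale (raw or log), no alpha, no margin and no confidence interval. The section also plans tabular and graphical summaries and a NONMEM population model, but describes no test of dose linearity within that model.

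On the data available, section 13.3 says: "With 2-3 likely dose levels, the total sample size and the study duration are expected to be 12-18". Section 5.1.1.2 starts at 50 mg/m² bid, has 65 mg/m² as level 2, and allows level 2 to be skipped: "we propose to proceed from dose level 1 directly to dose level 3 (85 mg/m² bid", conditional among other things on tolerance of the starting level. PK sampling is required in Phase I and optional in Phase II (section 9.1.1). Section 8.1 describes the drug's PK as linear.

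**The concern.** There are two separate problems.

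**Which parameters.** Under linear kinetics AUC rises in proportion to dose, so AUC/dose should be flat. Vc/F, Ke, t1/2 and CL/F do not depend on dose, and CL/F already contains it (Dose/AUC). An analyst who applied the sentence to the whole preceding list would divide four flat quantities by dose. That builds in a gradient of up to 85/50 = 1.7-fold, which the ANOVA would then tend to find.

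**What the test can show.** Even for AUC alone, a test of no difference in a small sample cannot support proportionality. It returns a p-value rather than the size of any departure, and with three levels it treats dose as unordered.

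Plasma PK is a Phase I primary objective (section 1.1), and section 2.4.3 calls these data critical for planning a phase III study. An answer that is misleading or uninterpretable would carry into that planning.

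**Working it through.** The plan states no power, effect size or alpha for this analysis, so there is no figure of its own to reproduce.

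**Inputs from the documents**
- Doses 50, 65 and 85 mg/m² (section 5.1.1.2).
- 12-18 Phase I patients over 2-3 levels (section 13.3), so about 6 per level, or 4 per level for 12 patients over three.
- AUC variability from Table 2, section 2.2.3.2: "1.55 1.05 ± 0.42 1.87 ± 0.49 0.99 ± 0.37". The CVs are 0.42/1.05 = 40%, 0.49/1.87 = 26% and 0.37/0.99 = 37%, all from very small groups.

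**Assumptions not in the documents**
- Alpha 0.05, log-normal data and equal groups.
- Table 2 CVs apply at 50-85 mg/m².
- CV of 20-40% for the dose-independent parameters.
- A log-log slope of 1.5 as the departure of interest. Dose-normalised AUC is then 1.7^0.5 = 1.30 times as high at 85 as at 50 mg/m².

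**Formulas (log scale)**
- SD = √ln(1+CV²): 0.198, 0.256, 0.294 and 0.385 for CV 20%, 26%, 30% and 40%.
- Sxx = Σ n(ln dose − mean ln dose)². For 6+6 at 50/85: 12 × (0.531/2)² = 0.845. For 6 per level at 50/65/85: also 0.845, because 65 lies almost at the mid-point in logs. For 6+6 at 50/65: 12 × (0.262/2)² = 0.207.
- ANOVA power is the upper tail of a noncentral F. For a flat parameter divided by dose, λ = Sxx/SD². For AUC with slope b, λ = (b−1)²·Sxx/SD².

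Worked example, three levels of 6, CV 40%, slope 1.5: λ = 0.25 × 0.845/0.385² = 1.42. The critical value of F(2,15) is 3.68, and power is 15%.

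**Result 1: a truly dose-independent parameter divided by dose (nominal rejection 5%)**

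| Design | CV 20% | CV 30% | CV 40% |
|---|---|---|---|
| 50/65, 6+6 | 55% | 29% | 19% |
| 50/85, 6+6 | 99% | 81% | 58% |
| 50/65/85, 4 each | 82% | 47% | 30% |
| 50/65/85, 6 each | 97% | 72% | 47% |

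If only AUC is normalised and is truly proportional, simulated rejection was 4.5-4.9%: no artefact.

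**Result 2: AUC only, slope 1.5**

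| Design | ANOVA power, CV 26% | ANOVA power, CV 40% | 90% CI half-width for slope, CV 26% to 40% |
|---|---|---|---|
| 50/65, 6+6 | 13% | 8% | 1.02 to 1.54 |
| 50/85, 6+6 | 37% | 19% | 0.50 to 0.76 |
| 50/65/85, 4 each | 18% | 11% | 0.62 to 0.93 |
| 50/65/85, 6 each | 29% | 15% | 0.49 to 0.73 |

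The half-width is t(0.95, N−2)·SD/√Sxx. Example, 6+6 at 50/85, CV 40%: 1.812 × 0.385/√0.845 = 0.76.

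**Result 3: what a power model adds.** With three levels of 6, the one-degree-of-freedom slope test has 39% power (CV 26%) or 20% (CV 40%), against 29% and 15% for ANOVA. With two levels, testing slope = 1 is the same test as ANOVA on log(AUC/dose), so there is no gain in power.

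**The case against.** The strongest reply is that the sentence concerns dose proportionality, so the parameters it normalises are naturally those expected to scale with dose, here AUC. The list before it is open-ended and does not define what is normalised. This largely stands. A reader might infer that the plan will manufacture dose effects in t1/2, Ke, CL/F and Vc/F. The documents do not support that, because they nowhere say those four will be divided by dose. What remains is that nothing in the text excludes it.

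A second reply is that any power figure rests on a chosen departure and CV. That also stands. A reader might settle on a single low range such as 12-24% for AUC. That range belongs to a raw-scale ANOVA at slope 1.5 and the largest Table 2 CV, including a scenario with an assumed 40 Phase II PK patients. On the log scale the same three configurations (6+6, three levels of 6, and 6+40) give 15-34% at CV 40% and 29-64% at CV 26%. A 2-fold change in dose-normalised AUC would be found with 71-97% power with three levels of 6.

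Third, the plan does not say that p>0.05 will be read as proportionality, and it sets no decision rule on this test: dose selection rests on DLTs (section 13.1.1). NONMEM and descriptive summaries are planned as well. All of this is correct and limits the harm. It does not make the ANOVA informative, since even on the AUC-only reading it reports no estimate and no interval.

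**Conclusion.** The point holds in a limited form. The sentence is underspecified, and on a literal reading it could create false dose effects in up to four parameters (47-99% rejection with 6 per level spanning 50-85 mg/m², 19-55% at 50/65 only, for assumed CV 20-40%). On the more natural AUC-only reading that artefact is absent. The test would still miss a slope of 1.5 in most trials of the expected size: power is 15-29% with three levels of 6 and 19-37% with 6+6 at 50/85, for CV 40% to 26%. A non-significant result is therefore not evidence of proportionality. These figures depend on the assumed alpha, departure and log-normality, and on CVs from very small groups. With no trial decision tied to the test, this is a cheap improvement of minor to moderate importance.

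**What to change.** Replace the sentence in section 13.2.3 with three statements:

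1. Dose proportionality of AUC will be assessed by a power model, regressing log AUC on log dose over all Phase I and available Phase II PK patients, and reporting the slope with a 90% CI.
2. CL/F, Vc/F, Ke and t1/2 will be compared across dose on the log scale without dividing by dose, or dose will be tested as a covariate on CL/F in the NONMEM model already planned.
3. Proportionality will not be inferred from p>0.05.

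The cost is a short text change, with no new data. The drawback is that the interval will be visibly wide: a half-width of about 0.5-0.76 on the slope with 6 per level spanning 50-85 mg/m², and 1.02-1.54 if only 50 and 65 mg/m² are studied. Optional Phase II samples help only in part, because they add patients at a single radiation-phase dose. The change makes the uncertainty explicit and closes off the possible artefact; it does not cure the small sample.

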13.3 Projected Accrual Rate and Study Duration

Phase I

The projected accrual rate is 1.5-2.5 patients per month, based on knowledge of the member institutions and their commitment to the Consortium. With 2-3 likely dose levels, the total sample size and the study duration are expected to be 12-18 and about 1.5-2.0 years, respectively. The estimated duration incorporates the planned accrual suspensions for routine toxicity monitoring.

Phase II

The projected accrual rate is 1.5-2.5 patients per month, based on knowledge of the member institutions and their commitment to the Consortium. The total sample size and the study duration are expected to be approximately 60 patients and about 2-3.5 years. The table below is for both phases (Phase I and II combined)

I ab						
Expected: Nun	iber of Subjects					
Ethnic Category		Sex/Gender	•			
Ethnic Category	Females	Males	Total			
Hispanic or Latino	5	5	10			
Not Hispanic or Latino	33	23	56			
Ethnic Category: Total of All Subjects *	38	28	66			
Racial Categories						
American Indian / Alaska Native	1	0	1			

Table 21	
----------	--

Asian	2	2	4
Native Hawaiian or Other Pacific Islander	0	0	0
Black or African American	5	3	8
White	30	23	53
Racial Categories: Total of All Subjects*	38	28	66

13.4 Analysis of Secondary Endpoints

13.4.1 Statistical Analysis of Imaging Studies:

We will describe and summarize the observed values of the proposed quantitative imaging parameters, namely rCBV, permeability (K^{trans}, v_p , and v_e values) and ADC as well as changes in these parameters via descriptive statistics and plots. If serial values are available from adequate number of patients to make such models meaningful, we will also entertain the use of mixed effects models in modeling changes in these parameters. Depending on the number of pseudoprogression calls observed, we may also explore associations between these imaging parameters and pseudoprogression vs. true progression via appropriate models or simply via summary statistics and descriptive plots within and across patients. The assessment of true vs. pseudo progression will be based on the tumor measurements from subsequent scans. For the primary objective regarding pseudoprogression, we will provide 95% confidence interval estimates of the proportion of patients determined to have experienced pseudoprogression.

13.4.2 Statistical Analysis of Biologic Correlates

13.4.2.1 NHEJ and PARP Activity

PARP inhibition in PBMCs will be measured as a ratio of pre/post-treatment values and will be summarized by dose level via exact confidence intervals. The values observed in this trial will be contrasted to the values reported in adults.

Provided adequate number of events is observed among patients who participate in biology studies to make such analyses feasible, we will utilize Cox models to explore associations between the molecular parameters from correlative biology aims 1-2, namely PARP and NHEJ activity or γ -H2AX levels and PFS and OS. Associations between these parameters and objective response may also be explored provided a large enough number of responses are observed. Otherwise correlations between PARP and NHEJ activity or γ -H2AX levels with radiographic response and clinical outcome will be summarized descriptively.

13.4.3 Urine Biomarkers

Comparison of Urine Biomarker Levels in Patients vs. Controls:

In order to determine whether the levels of these urinary biomarkers are elevated in DIPG patients, we will compare median levels for tumor patients to levels in healthy age- and gendermatched controls using the Mann-Whitney U-test. Despite the presence of matched controls, Mann-Whitney U-test allows us to utilize a conservative approach compared to the Wilcoxon signed-rank test since matching by age and gender is done to reduce variability rather than to facilitate the use of methods for paired data. In addition, the percentage of patients and controls above the previously established cut-off values for each urinary biomarker will be compared using the chi-square test. Based on a preliminary power analysis for this chi-square test a sample

size of 58 brain tumor patients and 58 controls will provide 80% power with a conservative twosided alpha level of 0.01 in capturing a difference of 30% between the groups with respect to each urinary biomarker. We will also utilize ROC analysis for each biomarker in exploring various cut-points for differentiating between the control subjects and DIPG patients. Multivariable logistic regression models coupled with ROC analyses will be used to select a combination of these biomarkers in an attempt to improve their collective performance as a classifier.

Longitudinal Assessment of Changes in Biomarker Values and Their Association with Outcome: Using the data for patients who progress, for each biomarker we will compare the levels at baseline with levels at progression as determined by MRI to assess whether the biomarker values change and if so by how much. This will be done via Wilcoxon signed rank test and exact confidence interval estimates of the percent change. We will also tabulate the percentage of patients who have biomarker levels above the previously established cut points for each biomarker at baseline and at the time of progression. We will investigate whether the percentage of patients who are above/below the cutpoints for each of the biomarkers is different between baseline and time of progression via the McNemar's test. Provided adequate number of responses is present to make such analyses meaningful, we will also perform similar analyses comparing biomarker levels at baseline and at the time of response.

Time-to-event data will be analyzed using the Kaplan-Meier product-limit method and by the log rank test to compare the PFS and OS distributions of patients with biomarker values above and below the specified cut-off values at baseline.⁵² Provided adequate number of events exist to make such an exercise informative, will also utilize multivariable Cox proportional-hazards regression model with each of the 8 urinary biomarkers as time dependent predictors and relevant covariates including age and gender to explore associations with PFS and OS.⁵³

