2.4.4.1 Preliminary data

We reported the first demonstration of the utility of urinary biomarkers in brain tumors, including the use of molecules specifically related to the regulation of vascular stability⁴³ and recently published a proof-of-principle case series, that specifically evaluated the ability of a panel of urinary biomarkers such as MMP-2, MMP-9, NGAL and VEGF (See Figure 4 and **Table 6** and **Table 7**).⁴⁴ The results of this series support the premise that levels of urinary biomarkers can not only predict the presence of brain tumors but also that they change in response to effective surgical therapy (see Figure 5).

We have subsequently identified additional biomarkers that can be detected in urine in association with pediatric brain tumors. These new markers (HB-EGF, EGF, HGF and TIE-2) allow for greater sensitivity in identifying the presence of disease. Specific to this project, these markers have been evaluated in pediatric patients with various subtypes of high grade glioma, including both GBM and anaplastic astrocytoma.

Table 6								
Demographics, MMP's and VEGF for Brain Tumor Patients and Controls								
Variable	Contro	ol Group ((n=23)	Brain T	`umor Group	o (n=28)	Р	
	Median	IQR	Range	Median	IQR	Range		
Age, yr	22	4-55	0-71	32	8-58	1-73	0.37	
MMP-9	0	0-0	0-6	0.6	0-5.7	0-294	< 0.001*	
MMP-9/NGAL	0	0-0	0-12.8	0.8	0.2-1.0	0-1.1	< 0.001*	
MMP-2	0	0-0	0-3	4.3	0.8-8.8	0-27	< 0.001*	
VEGF	25	0-250	0-391	753	451-957	25-4462	< 0.001*	
Female sex, no. (%)	11(48)				13 (46)		0.92	

T 11 (

Table '	7
---------	---

Results of Receiver Operating Characteristic (ROC) Curve Analysis and Diagnostic Performance Indices of MMP-2 and VEGF							
	01 NIN	P-2 and VEGF					
Biomarker	AUC	95% CI	P value				
MMP-2 (ng/ml)	0.894	0.800-0.987	< 0.0001				
VEGF (pg/L)	0.965	0.913-0.999	<0.0001				
Cutoff Points	Sensitivity (95% CI)	Specificity (95% CI)	Accuracy (95% CI)				
MMP-2 >0.4 ng/ml	82.1 (65.2-94.0)	95.7 (78.1-99.9)	88.2 (76.1-95.6)				
VEGF >350 pg/L	95.2 (76.2-99.9)	89.5 (66.9-98.8)	92.5 (80.0-98.5)				

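### Section 13.4.3 derives urine cut-points and a marker combination in the trial patients and banked controls and plans no optimism correction, so their accuracy would be overstated

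*Combined protocol and SAP*

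**What the plan says.** Section 13.4.3 plans four comparisons of patients with age- and sex-matched banked controls:

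- a Mann-Whitney test of marker levels;
- a test at fixed thresholds: "the percentage of patients and controls above the previously established cut-off values for each urinary biomarker will be compared using the chi-square test";
- a ROC analysis of each marker to explore possible cut-points;
- a classifier: "Multivariable logistic regression models coupled with ROC analyses will be used to select a combination of these biomarkers".

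The sample size is attached to the second item only. A "size of 58 brain tumor patients and 58 controls will provide 80% power" at a "conservative twosided alpha level of 0.01", for "capturing a difference of 30% between the groups with respect to each urinary biomarker". The rates above the cut-off behind that figure are not given.

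Section 9.1.4.5 says that eight markers are measured. MMP-2, MMP-9 and MMP-9/NGAL are read blinded by zymography as positive or negative, and all eight are quantified by ELISA. Table 7 in section 2.4.4.1 prints two numeric cut-offs, "MMP-2 >0.4 ng/ml" and VEGF above 350 pg/L, with AUCs of 0.894 and 0.965. For HB-EGF, EGF, HGF and TIE-2 the text says "We have subsequently identified additional biomarkers that can be detected in urine in association with pediatric brain tumors" and prints no threshold.

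Section 1.3 lists the urine work as a secondary, exploratory objective. Section 9.1.4 makes participation optional.

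**The concern.** A cut-point chosen because it separates these patients from these controls, or a combination fitted to them, will look better in the same people than in new ones. Nothing in section 13.4 removes that gap. Secondary objective 8 asks whether urine markers could help to detect and track disease. An uncorrected AUC answers a different question: how well a rule can be fitted to the data in hand. Useless markers would still show an AUC well above 0.50.

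The missing cut-offs add a smaller problem. The chi-square test assumes an established threshold for each of eight markers, and the McNemar and log-rank analyses in the same section also use thresholds. The protocol prints two. A reader cannot tell which thresholds will be used for the other six, or that they are fixed in advance.

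**Working it through.** **1. The plan's own sample size.** Inputs from section 13.4.3: two-sided alpha 0.01 (z = 2.576), power 80% (z = 0.842), difference 0.30. The rates are not stated, so 20% v 50% is assumed. The mean rate is then 0.35, and without continuity correction:

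n per group = [2.576·√(2·0.35·0.65) + 0.842·√(0.20·0.80 + 0.50·0.50)]² / 0.30²
= [2.576·0.6745 + 0.842·0.6403]² / 0.09
= (1.737 + 0.539)² / 0.09 ≈ 57.6, rounded up to 58.

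The stated figure reproduces (power at 58 is 80.4%). It depends on the assumed rates: 30% v 60% needs 63, and 10% v 40% needs 48. It powers the fixed-threshold test and says nothing about the ROC search or the classifier.

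**2. Size of the optimism.** The marker effects are assumptions. Eight independent normal markers, all entered in an unpenalised logistic model, were fitted to n patients and n controls. Accuracy was scored in the same data and in 8,000 new subjects, with 400 data sets per setting.

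AUC optimism = apparent AUC − AUC in new subjects. The Table 7 AUCs convert to standardised differences through AUC = Φ(d/√2): d = 1.77 gives 0.894 and d = 2.56 gives 0.965.

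| Assumed truth | 58 v 58: apparent, new | Optimism at 58 | at 40 v 40 | at 30 v 30 |
|---|---|---|---|---|
| No signal | 0.647, 0.500 | 0.147 | 0.180 | 0.207 |
| One marker, d = 0.5 | 0.698, 0.595 | 0.103 | 0.137 | 0.171 |
| All eight, d = 0.25 | 0.736, 0.653 | 0.083 | 0.115 | 0.151 |
| Two markers, d = 0.75 | 0.804, 0.746 | 0.058 | 0.087 | 0.114 |
| Two markers at the Table 7 AUCs | 0.991, 0.977 | 0.014 | 0.024 | 0.032 |

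The smaller sizes matter because participation is optional. Table 21 expects 66 patients over both phases, so 58 needs 58/66 = 88% of them.

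**3. Cut-points.** Youden's J = sensitivity + specificity − 1, at the cut-point that maximises it. At 58 v 58:

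- one useless marker: apparent 0.111, true 0.000;
- eight-marker score, no signal: 0.284 v 0.000;
- eight-marker score, Table 7 AUCs: 0.934 v 0.837, a gap of 0.097.

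So even where the AUC is overstated by only 0.014, the sum of sensitivity and specificity is overstated by about 10 percentage points.

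**4. Printed thresholds.** Table 7 covers two of eight markers. Positive/negative zymography could serve as a fixed threshold for MMP-9 and MMP-9/NGAL (and MMP-2), but section 13.4.3 does not say that it will. That leaves VEGF with its printed value and four added markers with none.

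**The case against.** The strongest reply is that this is optional, exploratory work that feeds no treatment decision, stopping rule or survival conclusion, and that optimism is slight if the markers are as strong as Table 7 suggests. The first part stands and limits the weight of the point. The second is right for the AUC but not for the sensitivity and specificity at a searched cut-point. It also assumes what is to be tested: Table 6 shows that the earlier series had median ages of 32 years (tumour) and 22 years (controls), not children with DIPG. The full eight-marker fit is also an assumption, since the plan speaks of selecting a combination. Selection without correction is still optimistic, but the exact size would differ.

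Three stronger readings are tempting and are not supported:

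- *The chi-square test is invalid.* A reader might infer that ROC-optimal cut-points will fill the gap for the unprinted thresholds. In null simulations at 58 v 58 that would raise the type I error to about 11% at a nominal 1% (5.7% if only elevation in patients is searched). But the plan ties this test to prior cut-offs and describes the ROC work separately.
- *The other six markers have no prior cut-off.* The documents show only that none is printed. Zymography readings offer a route for two of the six, and figures and cited papers could hold others.
- *The logistic model will probably fail through complete separation.* With independent normal markers at the Table 7 AUCs and six noise markers, separation occurs in about 18% of data sets at 58 v 58 and about 50% at 40 v 40. At 58 v 58 other assumptions give 1% (only the 0.965 marker informative, others noise) to 58% (the other six each at AUC 0.70). It is possible, but not shown to be likely at the stated size.

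**Conclusion.** The point holds in a limited form. As written, section 13.4.3 would give upwardly biased AUC, sensitivity and specificity for any cut-point or combination derived in this trial. At 58 v 58 with eight markers, the AUC bias is about 0.01 if the Table 7 AUCs carry over and about 0.15 if there is no signal; at 30 v 30 the range is about 0.03 to 0.21. These sizes rest on independent normal markers and a full eight-marker fit. The direction of the bias does not depend on those details.

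Tests at thresholds fixed beforehand carry no such bias, so the chi-square comparison stands for any marker whose threshold is truly prior. The gap there is one of specification. The objective is secondary and exploratory, and the primary overall survival analysis is untouched.

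**What to change.** Add to section 13.4.3 that AUC, sensitivity and specificity of any cut-point or marker combination derived in this trial will be reported after optimism correction by bootstrap or repeated cross-validation, with marker selection and cut-point search repeated inside each resample. Apparent values may be shown beside the corrected ones if labelled as such.

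List for each marker the threshold and its source, fixed before the assay data are unblinded. The positive/negative zymography reading can serve where it applies. Limit the chi-square test to markers on that list, and rely on the Mann-Whitney test, already planned, for the rest. There is no need to confine the chi-square test to MMP-2 and VEGF. State the rates behind the sample size of 58.

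Penalised regression is a reasonable fallback if the groups separate completely, but it need not be mandatory.

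The cost is plan text and analysis code, with no added patients, samples or visits. The downside is that reported accuracy will be less favourable.
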